Preclinical pharmacokinetics

In adult rats and dogs, branaplam was moderately or completely absorbed. In rats there was some indication of first-pass elimination. Upon daily administration there was no accumulation of branaplam in adult animals.

In juvenile rats, an age-related change in PK was observed, with a ~3-5 fold decrease in branaplam plasma AUC on postnatal day 41 compared to postnatal day 7. After continued daily treatment (postnatal days 97 and 186) exposure levels increased but were comparable to day 7 values, i.e. 2-3 fold lower than the expected value if accumulation is taken into account. A reduction in systemic exposure with progressing age of the animals may be related to maturation of metabolizing enzymes and other physiological processes (e.g. hepatic blood flow). In juvenile dogs a similar but less pronounced decrease was observed in plasma exposure between postnatal day 28 and 56 (20-40% decline in AUC). These changes may be attributed to the maturation of drug metabolizing enzymes and/or transporters as well as tissue perfusion and permeability changes during growth and development in juvenile animals. Similar effects can be expected in humans over the first year to two years of life.

In juvenile mice and dogs, the brain to plasma exposure ratio was about 10, indicating that branaplam penetrated well into the brain. This is expected to decrease as a consequence of maturation of the blood brain barrier. As such, good central exposure is also anticipated in human infants, while a similar decrease in brain exposure may occur as infants grow.

The elimination of branaplam in rats occurred mainly via glucuronidation with subsequent excretion into feces. *In vitro* experiments indicated that UGT1A4, UGT1A7, and UGT1A9 were capable of branaplam direct glucuronidation. Experiments in human liver microsomes showed that CYP3A4 is the major enzyme involved in human hepatic metabolism of branaplam. Branaplam was also found to be a substrate of P-gp. Other transporters seem not to be involved in cross-membrane transport of branaplam.

Branaplam showed weak inhibition of CYP2C19, CYP2D6, and CYP3A4/5 (unbound IC $_{50}$ values of 9.9, 19, and 21 μ M, respectively) and did not inhibit transporters (BCRP, P-gp, OATP1B1, OATP1B3). Overall, it is thus thought that the drug-drug interaction potential with branaplam is low and infants with SMA type I are not expected to be on chronic polypharmacy.

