a: mean ± Standard Deviation (SD); b number of PK profiles considered; please note, that a patient provides several PK profiles to the analysis; c: AUC corresponds to the area under the plasma (or serum or blood) concentration-time curve from time zero to infinity [mass x time / volume] (AUCinf) after the first dose and the area under the plasma (or serum or blood) concentration-time curve from time zero, which is equal to the dosing time to 168 h [mass x time / volume] (0AUC0-168h) after multiple doses

Dose-normalized AUC and Cmax values across the age range from 2.5 to 58.5 months ranged from 595 to 2360 (h*ng/mL)/(mg/kg) and from 10.3 to 57.0 (ng/mL)/(mg/kg), respectively, and seemed to be comparable across the age range investigated. Linear regression analysis, which considered all dose-normalized exposure values, indicated a minor age-dependent increase with a maximum of 1.2 (AUC) and 1.4-fold (Cmax) increase across the observed age range. Similar assessment has been executed across the body weight range (5.11 kg to 16.3 kg). Comparable observations were made when dose-normalized AUC and Cmax values were correlated with the body weight range from 5.11 to 16.3 kg. Exposure values seemed to be comparable across the body weight range investigated. Linear regression analysis indicated a minor body weight-dependent increase of dose-normalized AUC and Cmax by 1.4 and 1.3-fold, respectively, considering the minimum and maximum observed body weight. No obvious impact of the administration method (feeding tube versus oral) was observed on both plasma exposure parameters, AUC and Cmax.

In Part 2 of present study, PK parameters were investigated across all observation periods at actual mean doses of 0.625 and 2.5 mg/kg, Table 1-2). Following oral branaplam administration across all observation periods, median Tmax values of branaplam in plasma ranged between 3.75 and 4 h at all observation periods (after 1 dosing, at month 3 and months 9). Thereafter, branaplam decreased slowly from plasma with mean apparent terminal elimination T1/2 values of 42.2 h and 46.0 h at the low and high dose level, respectively. AUC and Cmax values increased approximately with increasing dose in a dose-proportional manner. Mean apparent systemic clearance (CL/F) were 660 and 781 mL/h/kg and volume of distribution (Vz/F) values 40000 and 52400 mL/kg for 0.625 mg/kg and 2.5 mg/kg, respectively. Overall, all PK parameters were comparable to those observed in Part 1 (see above).

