of each dose level to ensure patient safety. A decision to dose escalate the next cohort will be made after safety data have been collected for 14 days following the first dose (14-day DLT window). PK will be used to confirm that there is no accumulation of the compound. If PK data show the potential for accumulation, the dosing frequency may be decreased. For Part 1, patients completing 13 weeks of treatment will be considered to have completed the study. Patients who are continuing to receive study medication follow the Assessment schedule-part1-Extended treatment period. The assessment schedule repeats until the patient discontinues the study or transfers to Part 3 the investigator agree that this is in the best interest of the patient.

Part 2 of the study did enroll new patients into one of 2 dose cohorts of 0.625 mg/kg and 2.5 mg/kg with once weekly dosing for 52 weeks. The branaplam dose was escalated in subsequent cohorts after 6 patients have been enrolled or at least 3 patients from the initial cohort have completed 13 weeks of treatment. After 52 weeks, patients may continue treatment in Part 3 of the study if in the best interests of the patient, as assessed by the investigator.

Part 3 of the study is long term safety and efficacy follow up of extended oral/enteral, once a week branaplam treatment. All patients who participated in Part 1 and Part 2 of the study and have completed at least 52 weeks of treatment, or more can continue receiving treatment with branaplam in Part 3 of the study.

Continuation of the treatment will be done at the dose assigned while in Part 1 or Part 2 of the study. However, if at any later time an interim analysis of Part 1 or Part 2 study data suggest one optimal dose considering existing safety as well as efficacy data, the dose patients are receiving might be adjusted while participating in Part 3 of the study protocol.

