3.5.5 Age effect

Branaplam PK is expected to change with age as a consequence of maturation of metabolizing enzymes (UGTs and CYP3A4) and transporters (Pgp). This may reduce the bioavailability, impact the distribution to the brain (Pgp) and/or increase the clearance, leading to a reduction of exposure. Therefore, the doses in both parts have to be adjusted either to the BSA (Part 1) or body weight (Part 1 extension, Part 2) as described in Section 5.1.2. Since BSA and body weight increases with age in infants, the effect of age on the PK will, at least partially, be compensated by the BSA/body weight adjustment. However, this may not completely compensate for the changes in metabolic and absorption/distribution processes. Therefore, PK samples have been and will be collected in all study parts every 3 to 6 months for assessment of PK exposure parameters (Part 1 and Part 2) and of steady state concentrations (Part 3). Results of all of these assessments will be evaluated for potential dose adjustments even on an individual basis to maintain the same exposure (AUC) as observed after the first dose.

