2.9.2 Accumulation ratio

Part 1

In subjects, who received the same dose in the first two treatment cycles of 3 months each, the parameters AUC0-168h for both observations and Cmax will be log transformed and used in an ANCOVA model with day as a factor, log dose as a covariate and day by dose interaction and subject as random effect. The LSMeans and their mean difference between treatment cycle 2 and Day 1 for each dose level, together with 90% confidence limit will be calculated from this model. These will be back-transformed to provide an estimate of the accumulation ratio with corresponding 90% CI.

Part 2

Accumulation ratio can be estimated as described for Part 1. Since no intra-individual dose escalation is planned, the accumulation will be estimated for each observation period versus first administration.

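### The accumulation ratio in SAP 2.9.2 mixes drug accumulation with any change in exposure as the infant ages, so it needs a different label and a companion ratio

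*SAP*

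**What the plan says.** SAP 2.9.2, Part 1, takes children who kept the same dose through the first two three-month cycles. Log AUC0-168h (on both occasions) and log Cmax enter an "ANCOVA model with day as a factor, log dose as a covariate and day by dose interaction and subject as random effect". What the plan then draws from this fit is a contrast between two occasions: "The LSMeans and their mean difference between treatment cycle 2 and Day 1 for each dose level". Back-transforming that contrast gives what the plan calls an "estimate of the accumulation ratio with corresponding 90% CI". Part 2 uses the same method, except that "the accumulation will be estimated for each observation period versus first administration". There is no term for age, weight or clearance.

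Protocol Section 3 (Study design) says for Part 1 that "PK will be used to confirm that there is no accumulation of the compound", and allows less frequent dosing if accumulation looks possible.

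On age, the protocol says two things that pull in opposite directions:

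- Section 3.5.5 states that "Branaplam PK is expected to change with age as a consequence of maturation of metabolizing enzymes". It expects lower exposure as a result, and warns that scaling the dose to weight or BSA may offset this only in part. Section 1.1.1 describes falling exposure in juvenile rats and a 20-40% lower AUC in juvenile dogs, and adds: "Similar effects can be expected in humans over the first year to two years of life".
- The Part 1 infant data in Section 1.1.1 show broadly similar dose-normalised exposure from 2.5 to 58.5 months of age, with a "minor age-dependent increase with a maximum of 1.2 (AUC) and 1.4-fold (Cmax) increase across the observed age range".

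SAP 2.9.3 relates the PK parameters to age and weight, using AUCinf after the first dose and AUC0-168h later. Nothing from that analysis enters the ratio in 2.9.2 or its interval.

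**The concern.** Within a child, study day and age advance together. A later-to-first exposure ratio therefore carries two effects: carry-over between weekly doses, and any change in clearance or bioavailability as the child matures. With no comparator and no closer occasion in the contrast, the model cannot separate them. Adding age as a covariate would hardly help, because each child's change in age equals the change in day.

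If exposure falls with age, real carry-over is hidden and the ratio reads as no accumulation. If exposure rises, ageing is reported as accumulation. In either case the 90% CI describes the combined ratio. This matters because the carry-over expected from the half-lives is small, so a modest drift is of similar size.

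**Working it through.** The documents give no numerical accumulation ratio, so there is no plan figure to reproduce. Protocol 1.1.1 reports only that no obvious accumulation was seen between cycles 1 and 2 in a subset.

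**Inputs**
- Dosing interval: 168 h (weekly).
- Mean half-lives (Protocol 1.1.1): 37.4 to 59.3 h in Part 1; 42.2 h (0.625 mg/kg) and 46.0 h (2.5 mg/kg) in Part 2.
- Part 2 CL/F: 660 and 781 mL/h/kg. Vz/F: 40000 and 52400 mL/kg. Mean Cmax: 21.7 and 77.4 ng/mL (Table 1-2).
- Later profiles: Day 92 (91 days, about 3 months after Day 1) and Day 274 (273 days, about 9 months), from Tables 7-2 and 7-3.
- Part 1 age slope: at most 1.2-fold (AUC) and 1.4-fold (Cmax) over 58.5 − 2.5 = 56 months.

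**Consistency of the inputs.** ln2 × (Vz/F)/(CL/F) gives 0.693 × 40000/660 = 42.0 h and 0.693 × 52400/781 = 46.5 h, close to the stated 42.2 and 46.0 h.

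**What the contrast estimates.** For linear PK with a mono-exponential decline, Day 1 AUC0-168h = AUCinf × (1 − 2^(−168/T1/2)). At steady state, AUC0-168h equals the AUCinf that a single dose would give at that age. The ratio is therefore R × m, where R = 1/(1 − 2^(−168/T1/2)) and m is the change in dose-normalised exposure between the two ages.

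| T1/2 (h) | R | Exposure fall that brings the ratio to 1.00 (1 − 1/R) |
|---|---|---|
| 37.4 | 1.047 | 4% |
| 42.2 | 1.068 | 6% |
| 46.0 | 1.086 | 8% |
| 59.3 | 1.163 | 14% |

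Even at 59.3 h, two weekly doses reach 1 − 2^(−336/59.3) = 98% of steady state. Change that arises after the first few weeks is not accumulation.

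**Bias from the observed Part 1 slope, taken as linear**
- AUC: 0.2 × 3/56 = 1.1% at 3 months; 0.2 × 9/56 = 3.2% at 9 months.
- Cmax: 0.4 × 3/56 = 2.1% at 3 months; 0.4 × 9/56 = 6.4% at 9 months.

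At 9 months the AUC drift is 3.2/8.6 = 37% to 3.2/6.8 = 47% of the expected Part 2 excess. For Cmax, the steady-state pre-dose level is roughly Dose/(Vz/F) × R × 2^(−168/T1/2). This gives about 1.05 and 4.1 ng/mL, or 1.05/21.7 and 4.1/77.4, about 5% of Cmax. The 6.4% drift is at least as large.

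**Upper scenario.** If the juvenile-dog fall applied in full, m would be 0.8 to 0.6. The Part 2 ratio would be 1.068 × 0.8 = 0.85 to 1.086 × 0.8 = 0.87 for a 20% fall, and 0.64 to 0.65 for a 40% fall.

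**Simulation of the SAP model.** Settings were 24 children, two doses, T1/2 44 h (R = 1.076) and 300 runs. The log-scale SDs of 0.20 between and 0.15 within children are assumptions.

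| Change in exposure | Mean estimate | 90% CI coverage of 1.076 |
|---|---|---|
| none | 1.077 | 86% |
| 3.3% rise | 1.107 | 79% |
| 20% fall | 0.860 | 0% |

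The estimates track R × m. Coverage is below 90% even with no change, so 86% is the reference for the other rows.

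**The case against.** **The human data suggest a small effect.** Part 1 infants showed a minor rise with age, opposite to the animal pattern. A bias of 1 to 3% in AUC is small beside exposure CVs of about 22 to 41% (Tables 1-1 and 1-2). This stands, with one limit: a single straight line over 56 months could understate change in the first year, and the documents give no separate figure for that period.

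**A reader might infer that the plan would report ratios of 0.6 to 0.9 with intervals that almost never cover the true accumulation.** The documents do not support that as the expected outcome. It takes the whole juvenile-dog fall, applies it to contrasts as short as 3 months although the protocol speaks of one to two years, and relies on assumed variances and sample sizes. It is an upper scenario only.

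**SAP 2.9.3 already looks at age, with the right pair of AUC measures.** It does, and this reduces the gap to a label and a link. The link is still missing: a reader of the 2.9.2 ratio and CI is not told that maturation is included.

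**A reader might infer that a dosing-frequency decision depends on this ratio.** That provision belongs to the conduct of Part 1. The SAP serves the final database lock, enrolment is closed, and the Part 3 dose has been selected. No stated decision still depends on the ratio.

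**A first-dose AUCinf/AUC0-168h ratio is a prediction.** It is calculated before any repeat dose and could not reveal unexpected accumulation. This is right, so it cannot replace the observed ratio.

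SAP 2.9.1 is cited but not visible in the public text. What it says cannot be judged and is not held against the plan.

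**Conclusion.** The point holds as one of estimand and labelling. The 2.9.2 contrast estimates accumulation multiplied by the time/age change in exposure, and its 90% CI is a CI for that product. Expected accumulation is 1.05 to 1.16 (1.07 to 1.09 in Part 2), so a fall of about 6 to 8% would hide it at the Part 2 half-lives. The bias best supported by infant data is upward: about 1% (AUC) and 2% (Cmax) at 3 months, and 3% and 6% at 9 months.

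These figures assume linear PK, the reported mean half-lives and a linear age slope. The documents do not show that accumulation has in fact been masked or overstated. The analysis is secondary PK in a study described as non-confirmatory, so the weight is minor to moderate.

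**What to change.** In SAP 2.9.2:

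1. Keep the day-contrast model, but label its result *ratio to first dose (accumulation combined with time/age change)*.
2. Add the same model for AUC with first-dose AUCinf in place of Day 1 AUC0-168h, and report it as the *time/age change in exposure*. It equals 1 under linear, time-constant PK and otherwise estimates m. There is no such counterpart for Cmax, whose ratio stays combined.
3. Report alongside, as supportive only, the accumulation predicted from each profile's T1/2, or from first-dose AUCinf/AUC0-168h where the terminal-phase rule in Protocol 7.5.1 is met.
4. State that these results are read together with SAP 2.9.3.

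The cost is SAP wording and a little programming on parameters already derived; no new samples are needed. The downside is lost profiles, because those with adjusted R-squared below 0.75 have no AUCinf or T1/2. In Table 1-2, which pools all periods, AUC was available for 29 profiles against 38 for Cmax at 2.5 mg/kg, and for 28 against 29 at 0.625 mg/kg. As far as Table 7-3 can be read, late sampling after the first Part 2 dose is sparse, so T1/2 from the Day 92 and Day 274 profiles may be the more available source. The predicted ratio assumes linear PK and supplements the observed one.

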More detailed review of the safety events in this study are presented in the most recent Investigator Brochure.

Human pharmacokinetic data

In Part 1 of present study, PK parameters were investigated across all observation periods at actual mean doses of 0.299, 0.644, 1.30, 2.51, and 2.99 mg/kg (respective nominal doses: 6, 12, 24, 48, and 60 mg/m², Table 1-1). Following oral branaplam administration across all observation periods, median Tmax values of branaplam in plasma ranged between 2.97 to 4.00 h. AUC and Cmax values increased with increasing dose after a single dose or across all observation periods. Both exposure parameters were considered to increase in an apparent dose proportional manner across all observation periods with a slight deviation from the upper 90% confidence interval for Cmax, which was considered to be clinically not relevant. Considering plasma profiles across all observation periods, mean apparent systemic clearance (CL/F) and volume of distribution (Vz/F) values were comparable across the dose levels and ranged between 735 and 1050 mL/h/kg and between 45600 and 63400 mL/kg, respectively. Branaplam concentrations decreased in plasma with mean apparent terminal elimination T1/2 values ranging between 37.4 h and 59.3 h. No obvious accumulation was observed in a subset of patients comparing exposure parameters of treatment cycle 1 and 2 after administration of same dose at both cycles.

Table 1-1 Systemic exposure values of branaplam across all observation periods - Study CLMI070X2201 Part 1

Nominal dose	Actual dose ^a	Arit	hmetic mean ± SD (%CV	()	
(mg/m²)	(mg/kg)	n ^b	Cmax (ng/mL)	n ^b	AUC (h·ng/mL) ^c
6 mg/m ²	0.299 ± 0.0240	11	8.84 ± 3.58 (40.5)	10	413 ± 98.3 (23.8)
12 mg/m²	0.644 ± 0.0341	4	15.3 ± 4.10 (26.8)	4	761 ± 170 (22.3)
24 mg/m ²	1.30 ± 0.0858	6	37.8 ± 12.8 (33.8)	6	1340 ± 381 (28.5)
48 mg/m ²	2.51 ± 0.186	16	69.1 ± 15.7 (22.8)	11	3310 ± 850 (25.7)
60 mg/m ²	2.99 ± 0.159	52	96.5 ± 32.7 (33.9)	41	4280 ± 1030 (24.2)

All values were rounded to 3 significant digits;

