Only patients who meet the inclusion/exclusion criteria at screening will be eligible to proceed to the baseline visit.

For a full list of assessments, please refer to Table 7-1.

Baseline

Visit 2 (Day -7 to -3) and Visit 3 (Day -2 to -1)

Due to the limited blood volumes available in infants, the baseline assessments have been split across two visits. The baseline visit may be combined into one day if appropriate.

All baseline eligibility assessment results must be available and confirmed by the investigator prior to progression into the treatment period.

First dose - Visit 4 (Day 1)

Patients will attend the investigator site in the morning. They will remain at the site for at least 24 hours for safety monitoring, after which they will be discharged locally at the discretion of the investigator. Patients who do not live within 60 minutes travel from the site should be housed locally until the day 8 visit (Visit 8) either at family/friends, or in a hotel. After visit 8 they may return home until their next scheduled study visit.

Pre-dose assessments will be conducted according to Table 7-1.

Time of dosing will be collected in the eCRF and appropriate documentation of the patient specific dispensing process must be maintained. Dose administration should occur at approximately the same time of day at each dosing visit (morning or afternoon). The investigator should be in contact with the Sponsor before dosing to confirm that there is a 24 hour gap between patients receiving their first dose of study drug across all study sites. If two sites have patients scheduled for Visit 4 in the same week, they must be scheduled 24 hours apart, allowing for time zone variations.

Following study drug administration blood samples will be drawn for PK analysis at specified time points throughout the day.

Reflux precautions must be implemented post-dosing per local institutional standards.

For a complete list of assessments, please refer to Table 7-1 for the initial treatment period and to Table 7-2 for the extended treatment period.

PK collections – Visits 5, 6, 7 and 8 (Day 2, 3, 5 and 8)

PK blood collections and safety assessments will be performed per Table 7-1 during the initial treatment period and per Table 7-2 during the extended treatment period and after the transfer into Part 3 per Table 7-4.

Safety Review – Visit 8 (Day 8)

Safety assessments and respiratory function will be performed per Assessment Schedule.

a blood sample for PK will be obtained.

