5.2 Treating the patient

5.2.1 Preparation and dispensation

Branaplam will be administered to the patient via the following route of administration:

Part 1:

• Enteral (via a feeding tube) during the initial treatment period of 13 weeks

• Either oral or enteral during the following extended treatment periods. The decision of the route of administration will be performed by the Investigator depending on the patient's ability to swallow.

Detailed information on how the transition from enteral to oral administration should be performed are given in the Site Operations Manual.

Part 2:

- Enteral (via a feeding tube) for the first administration on Day 1
- Either oral or enteral for the rest of the study. The decision of the route of administration will be performed by the Investigator depending on the patient's ability to swallow.

The option to administer branaplam orally may be reconsidered based on emerging PK data or if oral administration of the investigational drug is not tolerated by the patient following 2 consecutive attempts and as documented by the Acceptability and Palatability Questionnaire (see Table 7-3 and Section 7.5.1).

In Part 1 and Part 2 of the study branaplam may be administered at the study site, or at the patient's home by a qualified clinician or parent / legal guardian.

See the Site Operations Manual for further details. Sponsor qualified medical personnel will be readily available to advise on trial related medical questions or problems.

Part 3:

- Similarly to Part 1 and Part 2 of the study, in Part 3 branaplam can be administered by oral or enteral application. The decision of the route of administration will be performed by the Investigator depending on the patient's ability to swallow.
- Patient will receive first dose at Visit 1 and continue weekly drug administration at home administrated by parents/caregivers or qualified personnel.
- At all of the visits where PK is collected the study drug administration should be performed at the site.
- Dispensation and return of study drug is described in Site Operations Manual

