7.5 Additional assessments

7.5.1 Pharmacokinetics

PK samples will be collected at the timepoints defined in the Assessment Schedule.

In order to better define the PK profile, the timing of the PK sample collection may be altered based on emergent data. The total blood volume drawn including safety, PK assessments will not exceed 10 ml per visit over 13 weeks treatment period in Part 2 and 8.2 ml per visit over a 13 week period in an Extended treatment period in Part 1. In Part 3, the sample volume will not exceed 10 mL per visit over 13 weeks.

Further details on sample collection, numbering, processing and shipment can be found in the Site Operations Manual and Laboratory Manual.

Pharmacokinetics (PK) of branaplam will be evaluated in all patients at all dose levels in Parts 1, 2, and 3. PK plasma samples for branaplam analysis from venous blood or capillary blood (approximately $75-200~\mu L$ blood per sample). Further details of PK plasma sample collection method and associated procedure can be found in the Site Operations Manual.

Branaplam will be determined by a validated LC-MS/MS method; the anticipated Lower Limit of Quantification (LLOQ) is 0.500 ng/mL for both analytes. Concentrations will be expressed in mass per volume units and will refer to the free base. Concentrations below the LLOQ will be reported as "zero" and missing data will be labeled as such in the Bioanalytical Data Report.

Part 1 and 2

The following pharmacokinetic parameters will be determined for branaplam using the actual recorded sampling times and non-compartmental method(s) with Phoenix WinNonlin (Version 8 or higher): C_{max}, T_{max}, AUC_{last}, AUC_{inf}, T1/2, Vz/F and CL/F from the plasma concentration-time data.

The linear trapezoidal rule will be used for AUC calculation. Regression analysis of the terminal plasma elimination phase for the determination of T1/2 will include at least 3 data points after Cmax. If the adjusted R^2 value of the regression analysis of the terminal phase will be less than 0.75, no values will be reported for T1/2, AUCinf, Vz/F, and CL/F.

Part 3

The following pharmacokinetic parameters will be determined for branaplam using the actual recorded sampling times with Phoenix WinNonlin (Version 8 or higher): C_{trough} and C_{4h} . Summary statistics will be calculated for these parameters.

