2.9.4 Comparison of dosing methods

Branaplam can be administered either *via* tube administration or orally. To test the impact of the dosing method on the systemic exposure, the exposure parameters AUC (AUCtau or AUC0-168h) and Cmax will be compared between both dosing methods. The comparison will be executed for each subject individually, who was treated with both methods. Since the number of oral administrations per subject is considered to be low, especially when compared to tube administration, proposed assessments might be not feasible for all subjects treated with both methods.

Two assessments will be executed (if feasible) for Parts 1 & 3:

- Exposure parameters across the complete study duration will be dose-normalized using unit mg/kg and summary statistics for each method executed. Box plot comparing the two dosing methods will be prepared for each PK parameter.
- Exposure parameters of two subsequent profiles, of which one was derived after tube administration and the other after oral administration, will be dose-normalized using unit mg/kg. The ratio will be calculated between tube administration and oral administration.

For Parts 2 & 3, the same will be executed (if feasible) but without dose-normalizing. Results will be computed and displayed for each dose individually.

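### SAP 2.9.2 forms the accumulation ratio from linear-trapezoid AUC0-168h and Cmax on unequal sampling schedules; in Part 1 the AUC bias is about as large as the accumulation at half-lives of 42–46 h, and Part 2 depends on whether a 48 h sample was drawn on Day 1

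*SAP*

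**What the plan says.** **Analysis.** For Part 1, SAP 2.9.2 states that "the parameters AUC0-168h for both observations and Cmax will be log transformed" and analysed by ANCOVA. The contrast of treatment cycle 2 with Day 1 is back-transformed to a ratio with a 90% confidence interval. For Part 2 the same method may be used: "Since no intra-individual dose escalation is planned, the accumulation will be estimated for each observation period versus first administration". Protocol 7.5.1 adds: "The linear trapezoidal rule will be used for AUC calculation".

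**Sampling times as printed.**

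| Occasion | Source | Times (h) |
|---|---|---|
| Part 1, Day 1 | Protocol Table 7-1; section 3.1, "Visits 5, 6, 7 and 8 (Day 2, 3, 5 and 8" | 0, 1, 2, 4, 8, 24, 48, 96, 168 |
| Part 1, later cycles | Protocol Table 7-2 | 0, 4, 24, 48, 168 |
| Part 2, Day 1 | Protocol Table 7-3, period 1 | 0, 1, 2, 4, (8 unclear), 24, 168; 48 blank |
| Part 2, weeks 14 and 40 | Protocol Table 7-3, periods 2 and 4 | 0, 4, 24, 48, 168 |

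**Route.** In SAP 2.9.4, "the exposure parameters AUC (AUCtau or AUC0-168h) and Cmax will be compared between both dosing methods". In Part 2 the tube is required only at the start: "Enteral (via a feeding tube) for the first administration on Day 1". In Part 1 it is used for the first 13 weeks (Protocol 5.2.1).

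The available text of neither document restricts these ratios to common times or mentions the mismatch.

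**The concern.** A straight line across an interval of exponential decline lies above the curve, so the linear rule overstates the area, and more so the wider the gap. If both members of a ratio carry the same gaps, the error largely cancels. Here they do not. Part 1 Day 1 splits the stretch from 48 to 168 h at 96 h; later profiles do not. Part 2 Day 1, as printed, spans 24 to 168 h in one step; later profiles split it at 48 h.

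The error is systematic, so the planned 90% interval would be centred on the wrong value. It matters because Protocol section 3 relies on PK to show that the drug does not accumulate, and Protocol 3.5.5 uses later exposure, judged against first-dose AUC, when dose adjustment is considered. The two parts could also appear to disagree merely because they were sampled differently.

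**Working it through.** **Inputs.** Dosing interval τ = 168 h. Terminal half-lives: Protocol 1.1.1 gives "mean apparent terminal elimination T1/2 values ranging between 37.4 h and 59.3 h" for Part 1, and 42.2 h and 46.0 h for the two Part 2 doses. Median Tmax is 3.75–4 h in Part 2. Cmax and AUC come from Protocol Table 1-2.

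**Reproducing the half-lives.** ln 2 × (Vz/F)/(CL/F) gives 0.693 × 40000/660 = 42.0 h and 0.693 × 52400/781 = 46.5 h, against 42.2 h and 46.0 h stated. The inputs agree to about 1%. The documents state no accumulation ratio to reproduce.

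**Error over one gap.** For pure exponential decline with rate k over a gap Δ, linear area divided by true area is (kΔ/2)(1 + e^(−kΔ))/(1 − e^(−kΔ)). At 46.0 h, k = 0.0151 per h. The 24–168 h gap gives 1.365 and the 48–168 h gap 1.259.

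**Whole profile, one compartment.** First dose: C(t) ∝ e^(−kt) − e^(−ka·t), with ka set so that Tmax = 4 h. Steady state: each exponential is divided by 1 − e^(−rate·168). True ratio = AUCinf / AUC0-168h of the first dose. The linear rule on each schedule then gives:

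| Half-life (h) | True ratio | Later AUC overstated | Part 1 Day 1 overstated | Part 1 planned ratio |
|---|---|---|---|---|
| 37.4 | 1.047 | 13.4% | 3.9% | 1.143 |
| 42.2 | 1.069 | 11.4% | 3.4% | 1.152 |
| 46.0 | 1.088 | 10.1% | 3.0% | 1.163 |
| 59.3 | 1.165 | 6.8% | 2.0% | 1.219 |

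| Half-life (h) | Part 2 Day 1 overstated, no 48 h | Part 2 planned ratio, no 48 h | Part 2 planned ratio, 48 h drawn |
|---|---|---|---|
| 42.2 | 28.2% | 0.929 | 1.053 |
| 46.0 | 24.6% | 0.961 | 1.073 |

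Check at 46.0 h: Part 1, 1.088 × 1.101/1.030 = 1.163; Part 2, 1.088 × 1.101/1.246 = 0.961.

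**Two compartments.** The shape is matched to Cmax/AUC (77.4/3470 at 2.5 mg/kg, 21.7/1020 at 0.625 mg/kg) and Tmax, with an assumed distribution half-life of 3–10 h. Example, with terminal half-life 46.0 h, distribution half-life 10 h and Tmax 4 h: true 1.068; Part 1 1.138; Part 2 0.854 (0.856 with an 8 h sample); Part 2 with 8 and 48 h 1.049. The unclear 8 h cell therefore hardly matters for AUC.

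**Range at 42–46 h, both models.** True 1.06–1.09; Part 1 1.13–1.16; Part 2 0.85–0.97 without 48 h and 1.04–1.07 with it.

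**Peak.** A later Cmax is in practice the 4 h value, while Day 1 takes the highest of several early samples. With every Tmax at 3–4 h and no noise there is no bias. With assumed variability in ka of 30–60% and residual error of 5–15%, the Cmax ratio is multiplied by 0.91–0.99, against a true ratio of about 1.05.

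**Common times.** At 42.2 and 46.0 h (one compartment), 0, 4, 24, 48, 168 h on both occasions gives 1.070 and 1.089; 0, 4, 24, 168 h gives the same. The true values are 1.069 and 1.088.

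**The case against.** **The Part 2 result hangs on one cell.** The period 1 PK row of Table 7-3 is damaged at 8 h. Protocol 7.5.1 requires three points after Cmax for a first-dose AUCinf. With a Tmax of about 4 h and neither 8 h nor 48 h drawn, only 24 and 168 h would remain. Yet Table 1-2 reports AUC for 28 of 29 low-dose profiles, with AUCinf used after the first dose. One further sample was therefore probably taken. This stands, but an 8 h sample alone would satisfy the rule, so it does not settle 48 h. A reader might infer that Part 2 will report falling exposure; the documents support that only if no 48 h sample was drawn.

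**Part 1 profiles may predate the current Table 7-2.** Dosing began in April 2015 and twelve patients had been treated by Amendment 4 (March 2016). Amendments 3 (November 2015) and 5 (August 2016) both changed the extended-period sampling. This stands: the figures describe the current schedule, and the actual bias may differ. Protocol 1.1.1 reports no obvious accumulation between cycles 1 and 2 in some Part 1 patients, but gives no ratio to compare.

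**Sampling times may be altered, and SAP 2.9.1 is redacted.** Protocol 7.5.1 permits changed times, and SAP 5.1.3 points to 2.9.1 for PK rules. A safeguard there cannot be excluded; none appears in the text available.

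**Tube versus oral.** A reader might infer that the whole of SAP 2.9.4 is confounded with schedule. It is not: tube dosing continues after Day 1, and pairs from later occasions share one schedule.

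**Consequence.** The study is non-confirmatory and the Part 2 ratio is optional. That limits the priority, not the bias.

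**Conclusion.** The concern holds in a limited form. At half-lives of 42–46 h and on the current Table 7-2 schedule, the Part 1 AUC ratio would be about 1.13–1.16 against a true 1.06–1.09. That upward bias is similar in size to the accumulation. It would be too strong to say that the bias matches the accumulation throughout: in the one-compartment runs it is +6.9% against +8.8% at 46.0 h, and about 0.3 of the accumulation at 59.3 h. In Part 2 the estimate is about 0.85–0.97 or about 1.04–1.07, according to whether 48 h was sampled on Day 1. For Cmax only the downward direction follows from the documents. SAP 2.9.4 is affected only for comparisons that use a Day 1 tube profile.

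The AUC figures assume noise-free profiles, PK that is linear and constant over time, a weekly steady state and, in the two-compartment runs, the assumed distribution half-life. Changes in exposure with age are not modelled.

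**What to change.** In SAP 2.9.2, and in 2.9.4 whenever a Day 1 profile is used, compute both members of each ratio from the sampling times that the subject's two occasions actually share. Nominally these are 0, 4, 24, 48, 168 h in Part 1 and 0, 4, 24, 168 h in Part 2, plus 48 h if it was drawn on Day 1. Use C4h for the peak ratio. Keep the full-schedule linear-trapezoid values in the descriptive tables.

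A log-down rule for all reported AUCs is not the remedy. It departs from Protocol 7.5.1 and leaves bias on unequal schedules: in Part 2 without a 48 h sample, the two-compartment ratio is about 1.02 against a true 1.06–1.08.

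The cost is a change of SAP wording and a rerun on existing concentrations. The downside is that the extra Day 1 samples go unused in these ratios, and C4h replaces Cmax there.
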